3.2. Safety Review Meetings

Safety Review Meetings (SRMs) will be held to review blinded safety data (such as AEs, vital signs, ECGs, and safety labs), and PK (if available) when 25%, 50%, and 75%, of the subjects are completed. Data to be reviewed may not necessarily be validated and cleaned (data query resolution may be pending). Data will be reviewed blinded (treatment assignment will not be revealed) unless unblinding is deemed necessary for the SRM committee.

The SRM members will include the regional Lead Investigator(s) or representative, CuraSen Chief Medical Officer, CuraSen Medical Monitor(s), and Clinical Research Study Manager. Additional members may be added as needed (e.g., statistician, PK scientist). The SRM committee will monitor subject safety and recommend whether to continue with dosing, to modify the protocol, to perform additional safety assessments and/or reviews, to delay or terminate subject enrollment, or to decrease and/or increase sample size based on emerging

safety data from this study or emerging safety, PK, and pharmacodynamics data from other ongoing and completed CuraSen studies.

3.3. Criteria for Termination of Study Medication

Dosing of the study medication will be terminated for any subject for whom the following circumstances apply:

- Any subject experiences a serious adverse event (SAE) that is assessed to be related to study medication
- Medical or ethical reasons affecting continuation of the study

Dosing of the study medication may be stopped if treatment-related AEs, changes in vital signs, ECG or clinical laboratory results are observed and these changes pose a significant health risk, in the opinion of the CuraSen Medical Monitor or Principal Investigator (PI).

A subject may be terminated at any point in time at the discretion of CuraSen Medical Monitor or PI.

3.4. Criteria for Suspension of Trial

The study will be stopped if either of the following occurs.

- One or more serious adverse events (SAEs) considered to be related to study medication; or
- Two or more severe or clinically significant adverse events (AEs) considered to be related to study medication

If following an internal safety review, it is appropriate to restart the study, a substantial amendment will be submitted to the appropriate regulatory authorities and Ethics Committee (EC). The trial will not restart in each region until the amendment has been approved by the regional regulatory authorities and ECs.

4. SELECTION AND WITHDRAWAL OF SUBJECTS

4.1. Study Participation

Approximately 40 subjects will be enrolled in this study. Approximately 20 subjects with RBD+PD or MCI will be enrolled in Cohort A. Cohort B of this study will include approximately 20 subjects with DLB or PDD. The number of subjects enrolled in each cohort may change as emerging data are reviewed from this and other studies.

All subjects must participate in the informed consent process and sign and date the informed consent before any study-related procedures are performed. Waivers for deviations from the eligibility criteria will not be granted.

4.2. Inclusion Criteria

A subject will be considered eligible for enrollment if all of the following criteria are met:

Cohort A

Subjects with RBD+PD:

1. Male or female subjects ≥ 40 and ≤ 80 years of age, at time of informed consent.
2. Subject diagnosed with Parkinson's Disease, as defined by the United Kingdom Parkinson Disease Brain Bank criteria, associated with REM sleep behavior disorder (RBD+PD), diagnosed according to the International Classification of Sleep Disorders, Third Edition (ICSD-3) (albeit documentation by polysomnography is not required) and positive response to the REM Sleep Behavior Disorder Single-Question Screen (RBD1Q).
3. Subject who is Modified Hoehn & Yahr \geq stage 1 and \leq stage 3 during "On" period as documented in the 3 months prior to Screening or completed at Screening.
4. Montreal Cognitive Assessment (MoCA) score ≥ 18 and ≤ 28 .

Subjects with MCI:

6. Male or female subjects ≥ 50 and ≤ 80 years of age, at time of informed consent.
7. Subjects who meet the criteria for amnesic Mild Cognitive Impairment (MCI) as per the National Institute on Aging-Alzheimer's Association core clinical criteria.
8. Montreal Cognitive Assessment (MoCA) score ≥ 18 and ≤ 26 .
9. No dementia according to the International Classifications of Diseases (ICD)-10 and Diagnostic and Statistical Manual of Mental Disorders (DSM)-IV.
10. A memory complaint reported by the subject or his/her partner, family member or caregiver.
11. A score of greater than or equal to one standard deviation below age and educational norms in the Digit Symbol Substitution Test (DSST) during Screening.
12. Cognitive decline not primarily caused by vascular, traumatic, or medical problems (alternative causes of cognitive decline are ruled out).

Cohort B

Subjects with Dementia with Lewy Bodies (DLB) or Parkinson's Disease Dementia (PDD):

14. Male or female subjects ≥ 50 and ≤ 80 years of age, at time of informed consent.
15. A diagnosis of dementia associated with Dementia with Lewy Bodies ([McKeith 2017](#)) or Parkinson's disease (PDD) ([Emre 2007](#)).
16. Documented cognitive fluctuations endorsed on the Dementia Cognitive Fluctuation Scale (DCFS) with a combined score of ≥ 8 in items 4, 11, 12 and 14 must be present.
17. Montreal Cognitive Assessment (MoCA) score ≥ 18 and ≤ 26 .
18. Subject having informant or caregiver throughout the study who will submit written consent to cooperate with this study, who routinely accompanies and/or stays with subject 12 hours or more a week, assists with treatment compliance, provides assessments and is able to escort the subject on required visits to study institution.
19. Subject who is Modified Hoehn & Yahr \geq stage 1 and \leq stage 3 during "On" period as documented in the 3 months prior to Screening or completed at Screening.
20. Stable concomitant medical and/or psychiatric illnesses in the judgement of the PI.

For ALL Subjects:

21. Unless confirmed to be azoospermic (vasectomized or secondary to medical cause), males must agree to use a male condom from Day 1 throughout the study when having penile-vaginal intercourse with a woman of childbearing potential who is not currently pregnant.

Note: Men with a pregnant or breastfeeding partner must agree to remain abstinent from penile-vaginal intercourse or use a condom during each episode of penile-vaginal penetration until after the Follow-Up Visit.
22. Females of childbearing potential (i.e., not postmenopausal or surgically sterile) who have a male partner must have a negative serum pregnancy test result and must agree to one of the following from start of Screening through 30 days after the last study medication administration:
 - a. use a reliable method of birth control (refer to [section 5.6](#)), or
 - b. monogamous relationship with a male partner of confirmed sterility, or
 - c. practice complete abstinence (refer to [section 5.6](#)).
23. Females of non-childbearing potential may be enrolled if it is documented that they are postmenopausal (refer to [section 5.6](#)).
24. Body weight greater or equal to 50 kg and body mass index (BMI) between 18 and 35 kg/m², inclusive at Screening.
25. Stable medical conditions for 3 months prior to Screening visit (e.g., controlled hypertension, dyslipidemia).
26. Willing to follow the protocol requirements and comply with protocol restrictions.
27. Capable of providing informed consent and complying with study procedures (completion of self-assessment rating scales and use of wearable devices). Subjects who are unable to provide consent may use a Legally Authorized Representative.

4.3. Exclusion Criteria

A subject with any of the following criteria will not be eligible for participation:

1. Subjects with poorly controlled hypertension despite lifestyle modifications and/or pharmacotherapy.
2. Subjects with pulmonary disease, including asthma if requiring the use of a β_2 -Adrenergic bronchodilator, or evidence of clinically significant moderate or severe pulmonary symptoms.
3. Clinical signs indicating syndromes such as corticobasal degeneration, supranuclear gaze palsy, multiple system atrophy, chronic traumatic encephalopathy, signs of frontotemporal dementia, history of stroke, head injury or encephalitis, cerebellar signs, early severe autonomic involvement, or Babinski sign.
4. Current evidence or history in past two years of epilepsy, focal brain lesion, head injury with loss of consciousness or meeting DSM-IV diagnostic criteria for psychotic disorders, such as Schizophrenia or Bipolar Disorder, or have unstable concomitant psychiatric symptomatology that is not believed by the Investigator to be associated with PDD or DLB.

5. Evidence of any significant clinical disorder or laboratory finding (or in the case of potassium levels below normal range) that renders the participant unsuitable for receiving an investigational drug including clinically significant or unstable hematologic, hepatic, cardiovascular, pulmonary, gastrointestinal, endocrine (excluding managed hypo and hyperthyroidism), metabolic, renal or other systemic disease or laboratory abnormality.
6. Participants with a history of malignant disease, including solid tumors and hematologic malignancies (except basal cell and squamous cell carcinomas of the skin that have been completely excised and are considered cured) within 5 years prior to Screening.
7. Any clinically significant illness or disease (apart from those typically associated with NDD) as determined by medical and surgical history, physical examination, 12-lead electrocardiogram (ECG) and clinical laboratory assessments conducted at Screening.
8. Clinically significant abnormalities of ECG, including QTcF > 450 ms, for males and QTcF > 470 ms for females, and/or HR < 50 beats per minute, or evidence of clinically significant bundle branch blocks, as indicated by 12-lead ECG in a supine position at Screening or during the Lead-In Period.
9. A calculated creatinine clearance of ≤ 60 mL/min according to the Cockcroft-Gault equation.
10. Current use of any prohibited prescription medication, over-the-counter medication, or herbal supplements/products (refer to [section 5.4](#)), during Screening or throughout study, unless approved by both the Investigator and the Sponsor Medical Monitor.
11. Known hypersensitivity to Spiropent (clenbuterol), Corgard (nadolol) or intolerance to lactose. Subjects with hereditary galactose intolerance (e.g., galactosemia, lactase deficiency or glucose galactose malabsorption) should be excluded.
12. Prior treatment with any investigational drug ≤ 90 days prior to dosing (Day 1), or ≤ 5 half-lives of the drug (whichever is longer), or current enrollment in any other study treatment or disease study except for observational studies.
13. Prior treatment with any β -AR agonists or β -AR blockers (includes oral medications, IV or inhaled) or any medications that impact adrenergic signaling within the last month prior to Screening.
14. Known or suspected alcohol or substance abuse within the past 12 months and/or positive test for alcohol or drugs of abuse at Screening or Day 1.
15. Suicidal ideation with acutal intent or plan (“Yes” answer on the C-SSRS ideation items 4 or 5) within 3 months prior to study Screening.
16. Positive screening test for hepatitis C antibody (HCV Ab) or current hepatitis B infection (defined as positive for hepatitis B surface antigen [HBsAg] at Screening). Subjects with immunity to hepatitis B (defined as negative HBsAg and positive hepatitis B surface antibody [HBsAb]) are eligible to participate in the study.
17. Positive screening test for human immunodeficiency virus (HIV).
18. Current infection with severe acute respiratory syndrome coronavirus 2 (SARS-CoV-2).

19. Contraindications to wearing the BioStamp digital device sensors, which include but are not limited to implanted pacemakers, defibrillators, or other active implantable devices, and known allergies.
20. Known hypersensitivities to adhesives or hydrogel.
21. Females who are breastfeeding.
22. Any other reason for which the PI considers it is not in the best interest of the participant to undertake the study.
23. Inability to undergo a clinical MRI of the brain due to claustrophobia, inability to lie supine for a prolonged time period, or other contraindications to undergoing an MRI of the brain including, but not limited to, pacemakers; implantable cardioverter defibrillators; cochlear implants; cerebral aneurysm clips; implanted infusion pumps; implanted nerve stimulators; metallic splinters in the eye; and, other magnetic, electronic or mechanical implants or clinical findings that in the judgment of the investigator would pose a potential hazard in combination with MRI. (NOTE: this is a procedural exclusion, not a study exclusion.)

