1.5. Rationale for CST-107 Dose Selection

CST-107 is included in this study to attenuate the peripheral effects commonly caused by β_2 -AR agonists which include increased heart rate, palpitations, tremors, decreases in potassium and increases in blood glucose. Previous CuraSen studies exploring low doses of CST-107 co-administered with 80 μg of CST-103 suggest that a 1 mg dose can attenuate these peripheral effects. This is in marked contrast to the usual initial dose for hypertension which is 40 mg CST-107 tablets once daily. The usual maintenance dose is 40 or 80 mg administered once daily and doses up to 240 or 320 mg administered once daily may be needed.

In the treatment of reactive airways disease, the use of a β -AR blocker is not normally recommended along with CST-103 in that the therapeutic effect of the agonist can be antagonized and would risk triggering a severe bronchospasm in patients with asthma. Since this study does not include patients with reactive airways disease and CST-103 is not being used for its bronchodilatory properties, this contraindication is not applicable to this study.

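### Protocol 1.5 sets the bronchospasm risk aside because no reactive airways disease is enrolled, but exclusion 2 does not clearly bar current asthma managed without a beta-2 bronchodilator

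*Protocol*

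**What the plan says.** Section 1.5 of the protocol discusses giving a beta-blocker with CST-103 in reactive airways disease. It says this is not normally recommended, because the agonist's benefit could be blocked and because it "would risk triggering a severe bronchospasm in patients with asthma". It then gives two grounds for proceeding: "Since this study does not include patients with reactive airways disease and CST-103 is not being used for its bronchodilatory properties", and so "this contraindication is not applicable to this study".

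Exclusion 2, worded the same in the synopsis and in section 4.3, removes "Subjects with pulmonary disease, including asthma if requiring the use of a" beta-2 adrenergic bronchodilator, "or evidence of clinically significant moderate or severe pulmonary symptoms". No other criterion names asthma or reactive airways disease.

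On dose, section 1.5 compares the 1 mg of CST-107 used here with ordinary practice: "This is in marked contrast to the usual initial dose for hypertension which is 40 mg CST-107 tablets once daily". Section 7.2 has CST-107 1 mg and CST-103 80 µg taken together once daily for 14 days in the active period. Section 7.2.1 puts the active period in both treatment sequences.

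**The concern.** Section 1.5 rests a safety conclusion on a statement about who is in the study. That statement is only as good as the eligibility criteria behind it. Exclusion 2 attaches a treatment condition to asthma, so a site could read it as leaving in a subject whose current asthma is mild or stable and managed without a beta-2 bronchodilator. Such a subject belongs to the group section 1.5 takes to be absent, and would receive CST-107 in whichever sequence was assigned. What is at stake is the safety of any such subject. No endpoint, model or sample size figure depends on it.

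**Working it through.** There is no plan figure to reproduce. The check sets the texts side by side.

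**Step 1. Match the grounds in section 1.5 to the harms it names.**

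- Harm (a): the agonist's therapeutic effect is blocked. The second ground, that CST-103 is not used here as a bronchodilator, answers this.
- Harm (b): severe bronchospasm in a person with asthma. The second ground does not answer this, because the harm does not depend on why CST-103 is given. Only the first ground, the absence of reactive airways disease, answers it.

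So for bronchospasm the argument depends on the criteria making the first ground true.

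**Step 2. Run one test subject through the criteria.** Take current mild or stable asthma, no need for a beta-2 bronchodilator, none used in the month before Screening, and no clinically significant moderate or severe symptoms. The asthma might be untreated or on a non-adrenergic controller; inhaled corticosteroids are not on the prohibited list in section 5.4.

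- *Exclusion 2, asthma clause:* not met on the natural reading, because the treatment condition is not satisfied.
- *Exclusion 2, symptom limb:* not met, because it needs moderate or severe symptoms.
- *Exclusion 5:* met only if the disorder is one "that renders the participant unsuitable for receiving an investigational drug including clinically significant or unstable hematologic, hepatic, cardiovascular, pulmonary, gastrointestinal" and so on. This is a judgement.
- *Exclusion 7:* "Any clinically significant illness or disease (apart from those typically associated with NDD) as determined by medical and surgical history, physical examination". Met only if the asthma is judged clinically significant.
- *Exclusions 10 and 13, and section 5.4:* these act on drugs taken, not on the diagnosis. Not met.
- *Exclusion 22:* investigator's view of the subject's interest. A judgement.
- *Inclusion 25:* admits medical conditions stable for 3 months, with no exception for respiratory disease.

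The subject meets no express exclusion. Whether the subject is kept out turns on the investigator's judgement under 5, 7 or 22.

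**Step 3. Put the exposure in proportion.**

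- Dose relative to the usual starting dose: 1 mg / 40 mg = 0.025 = 2.5%.
- Scheduled CST-107 doses for a completer in either sequence: 14 days × 1 capsule = 14, each taken with 80 µg of the beta-2 agonist CST-103.

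The documents give no asthma prevalence in the recruited population and no bronchospasm rate at 1 mg, so neither a count of subjects nor a probability of harm can be derived.

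**The case against.** The strongest reply is that exclusion 2 opens with pulmonary disease in general and offers asthma only as an example, so all asthma is already out. That reading is possible, and it means one cannot say flatly that the criterion bars asthma only when a bronchodilator is needed or symptoms are marked. But it leaves the treatment condition with almost nothing to do, and a site would reasonably take the condition as deliberate. At best the text is ambiguous on the point section 1.5 relies on.

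A second reply is that section 1.5 concerns patients being treated for reactive airways disease, which is the group exclusion 2 names, and concerns co-administration rather than CST-107 alone. This narrows the mismatch. It does not remove it, because the bronchospasm clause refers to patients with asthma without qualification.

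A third reply is that the backstops are real. That is right. Exclusions 5 and 7 are mandatory once judged to be met, and section 4.1 allows no waivers. Exclusion 13 removes recent beta-agonist users, inhaled use included. What remains is a subject whose asthma the investigator judges neither significant nor a reason against the drug. An investigator told in section 1.5 that the contraindication does not apply has less prompting to judge otherwise.

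Last, the hazard at 1 mg with a beta-2 agonist may be small, and the Investigator Brochure may support that. This bears on the size of the risk. It does not make section 1.5 and exclusion 2 consistent.

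**Conclusion.** The point holds as a minor patient-safety inconsistency. Section 1.5 disposes of bronchospasm by a premise that exclusion 2 does not clearly secure. The gap is narrow: current mild or stable asthma, managed without a beta-2 bronchodilator, and not caught by the investigator's judgement. The risk is tempered by a scheduled dose at 2.5% of the usual starting dose and by the co-administered agonist. Remote or resolved asthma is not part of the point.

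Three stronger readings are tempting, and the documents do not support them:

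- A reader might infer that the trial admits asthma freely. It does not, given the general words of exclusion 2, the judgement-based criteria and the drug-use rules.
- A reader might infer that a subject in the gap could use a reliever only as a protocol deviation. Exclusion 10 provides for otherwise prohibited medication that the Investigator and Medical Monitor both approve.
- A reader might link this wording to the dosing-termination and study-suspension rules in sections 3.3 and 3.4. Those rules follow any related serious event, so they say nothing particular about this criterion.

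The conclusion rests on the natural reading of exclusion 2 and on the one protocol supplied. The Investigator Brochure and the other regional protocol mentioned in SAP section 2.1 were not available.

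**What to change.** In the synopsis and in section 4.3, remove the treatment condition from exclusion 2, so that the asthma clause covers current asthma or other reactive airways disease regardless of treatment. Leave the opening words and the symptom limb as they are. Make the same check in the other regional protocol. Review enrolled subjects against the medical history already recorded, which under section 5.3.1 notes whether a condition is ongoing. Refer any subject found to the investigator and Medical Monitor, who already have discretion to act under section 3.3.

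If the sponsor prefers to keep current mild asthma eligible, section 1.5 should instead stop claiming that reactive airways disease is absent and say why the risk is acceptable at 1 mg with CST-103. Whether to bar remote, resolved asthma is a clinical choice for the sponsor.

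The cost is one sentence in two places, a check of a second document and a look at data in hand, with no new procedure. The downside is the possible loss of a few otherwise eligible subjects. The number cannot be estimated, and SAP section 2.1 already reports difficulty recruiting DLB and PDD.

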4.4. Enrollment Procedures and Randomization

4.4.1. Screening

After informed consent, all subjects will complete screening procedures and tests to establish eligibility during the Screening Period, which will be performed between Day -28 and Day -8. If a subject falls outside the Screening Period window, screening may be extended with prior approval by the CuraSen Medical Monitor. If extended beyond 21 days, some of the screening procedures and assessments may need to be repeated.

4.4.2. Subject Re-Screening

Subjects who have screen failed may be re-screened a second time if their eligibility characteristics have changed. Subjects who are re-screened must be assigned a new subject number within the Interactive Web Response System (IWRS). The screening process for such subjects must be discussed with the CuraSen Medical Monitor.

4.4.3. Randomization and Lead-In

Once all Screening tests and procedures are completed and all eligibility criteria are met, subjects will return to the clinic for randomization and begin the Lead-In Period. The IWRS will provide the randomization number. The Lead-In tests and procedures listed in the Schedule of Events will be completed within 14 days prior to Day 1 of Treatment Period 1. If subjects fall outside the Lead-In Period window, the Lead-In Period may be extended with prior approval by the CuraSen Medical Monitor.

